Gallbladder (GB) disease is extremely common, affecting 10% to 20% of White adults in the United States with the prevalence rising as high as 70% in specific ethnic groups. [1] Up to 5% of patients with gallstone disease become symptomatic within 1-year. [2] The incidence is greatest among obese people placing patients from racial and ethnic minority groups and those from low-income backgrounds at the greatest risk of disease. [3] Elective cholecystectomy is recommended for patients with symptomatic cholelithiasis or biliary colic. [4] Laparoscopic cholecystectomy is a safe and effective treatment that can be performed in the outpatient setting with complication rates ranging from 0.5-6.0%. [5]

Delayed treatment for symptomatic cholelithiasis and biliary colic often results in acute cholecystitis and related diseases that necessitate emergency surgery. [6] For example, patients waiting 20 weeks or more for elective cholecystectomy were more likely to undergo admission for emergency cholecystectomy than those waiting shorter times. [7] Emergent cholecystectomy results in worse outcomes with almost two-fold higher rates of conversion from laparoscopic to open, increased hospital length of stay by an average of over 5 days, increased rates of morbidity (8.8 vs 3.7%) and mortality (2.6 vs 0.5%), and higher costs (mean charge difference over \$6,000) when compared to elective cholecystectomy. [8-10]

Black and Hispanic patients, non-English primary language speakers, and those living in areas of greater social vulnerability are at increased risk of emergent GB surgery when compared with White, English primary language speakers, and those from well-resourced communities. [11-14] Barriers to timely consultation and surgery among historically marginalized communities include patient- and system-level factors. For example, work conflicts, limited paid time off, long clinic wait times, and limited ability to contact the surgical clinic often preclude the ability of patients with social vulnerabilities to seek a consultation or receive elective, operative care.[15-18]

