Social vulnerability (SV) is a complex concept with many definitions that are situationally dependent. For this proposal, we define social vulnerability by race, ethnicity, primary language, insurance, and income, five components known to be associated with disparities in care for patients with SGBD. Preliminary data show that the majority of the Penn Medicine PCSL population with SGBD meet our criteria for SV (Black race, 21% (n=1978); Hispanic 6% (n=565); non-English primary language 4% (n=376); low-income neighborhood 91% (n=8573)). Further, in preliminary data, when examining differences across racial groups, for example, Black PCSL patients treated within the past 6 months at PennMedicine were more likely to undergo emergent (vs elective) cholecystectomy than White patients (Black: 65% (76/117); White: 41% (125/303); p<0.001). Emergent operations are associated with worse outcomes and greater costs.

Using data abstracted from PennChart, we will conduct an observational study of patients seen within the PCSL and the those discharged from the Emergency Department with symptomatic cholelithiasis and biliary colic between Jan. 1, 2020 and Sept. 30, 2022. These data will allow us to examine quality of care in two dimensions, safety and efficiency, for patients treated in the community setting. While we focus our analysis on race, we will study the conditional effects of other dimensions of SV on quality. **To date, the reasons for and impact of delays in treatment of symptomatic GB disease in Black patients and those with other SV within our PennMedicine community is unknown.** To test a solution to the problems of time off work and transportation, we will enroll patients with SV seen in the PCSL clinics in a pilot designed to test telemedicine as a mechanism to improve timely access to surgical care. Health equity will be measured by rates of surgical consultation among patients with SV and timeliness of surgical consultation and treatment.

RESEARCH PLAN AND METHODOLOGY

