Overall Approach To address surgical health equity in patients with gallbladder disease, we will: 1) use regression models with interaction terms to examine racial disparities in surgical consultation and the conditional effects of SV factors on this relationship, 2) examine the marginal effects of social factors on outcomes, and 3) test a potential solution to surgical disparities, telemedicine. The first aim will be conducted in a retrospective observational study. Aim two will be performed as a pilot study of Penn Primary Care Service Line patients with SV. For this aim, we will pragmatically assign two groups to traditional care and telemedicine consultation and study the resultant outcomes. (See Conceptual Model above)

[figure not shown]
Research Team Our team has expertise in health services research, disparities research, general surgery and primary care. To conduct this innovative, scientifically rigorous mixed-methods study, we will also employ the services of research coordinators (DOS Clinical Trials Unit), data scientists (LDI-HEDAP), and statisticians (Center for Surgery and Health Economics). To ensure that the study will be conducted in a way that is acceptable to the community, we will recruit two patients from the PCSL to serve as advisors. Advisors will be compensated at \$50 per hour for an estimated total of 8 hours of work.

Impact This proposal has the potential to scale across practices, influence value-based purchasing agreements and enhance patient and clinician satisfaction. Moreover, the proposed aims will have a major impact on health equity by: 1) assessing the clinical and financial costs of delays, 2) identifying barriers to timely treatment, 3) testing a simple intervention to improve access to surgical health equity for patients with social vulnerabilities.

Outcomes of PCSL Patients with Symptomatic Gallbladder Disease (AIM 1)

Design A retrospective cohort study.

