Study Subjects and Eligibility Criteria Patients with a diagnosis of symptomatic cholelithiasis or biliary colic who were >18 years of age and enrolled in the Primary Care Service Line (PCSL) Registry in Clarity or evaluated and discharged from the Emergency Department (PAH, PPMC and HUP) between Jan. 1 2020 and Sept. 30, 2022 will be eligible for inclusion (data will be obtained for January 1 2020 to Dec. 31, 2022). The Primary Care Service Line (PCSL) covers more than 500,000 patients across the Penn Medicine catchment area including 12 contiguous urban, suburban, and rural counties in the tri-state area of PA, NJ, and DE (See Figure). The population is approximately 37.6% Black and 7.5% underinsured. Symptomatic cholelithiasis and biliary colic will be identified using International Classification of Diseases, Tenth Revision, Clinical Modification codes (ICD-10-CM). A 6-month “look-back” will be performed to confirm the first instance of disease. Patients with the following criteria will be excluded from study: 1) history of prior cholecystectomy 2) prisoners, or 3) contraindication to cholecystectomy including GB cancer, advanced cirrhosis and untreated coagulopathy.

Data Sources and Elements Clinical data will be abstracted from Clarity and financial data from the Horizon Performance Manager (HPM) dataset. This will allow real-world calculations of the value of care at Penn Medicine.

Definition of Social Vulnerability: Race will be the primary independent variable, given the established association between race and surgical disparities in the literature and preliminary data from Penn Chart. Ethnicity (Hispanic/non-Hispanic), primary language (English/non-English), insurance (Medicaid, Medicare, private, other) and low-income neighborhood (home zip code) will be identified in Clarity.

Covariates: Age, sex, comorbidities (defined by Elixhauser et al [28] using the index PCP visit and a 6-month look-back period), history of cholecystectomy, GB cancer, cirrhosis, coagulopathy and diagnostic imaging (US and CT SCAN) information will be obtained from Clarity. ICD-10 diagnosis codes will be used for clinical diagnoses. Date diagnosis add to chart, date of confirmatory imaging, date of discussion of treatment, date of referral to a surgeon and prisoner status will be obtained via direct chart review of PCSL notes within the 3-months following the initial diagnosis of SGBD. Access point will be designated as PCSL or Emergency Dept..

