Clinical Outcomes: Surgical consultation will be obtained from Horizon Performance Manager (HPM) via CPT codes for consultation. [29] Operative treatment will be determined using CPT and ICD-10-PCS codes for cholecystectomy as listed in HPM (CPT 47562, CPT 47563, CPT 47600, CPT 47605, CPT 56340, CPT 56341, ICD10 0FB40ZX, ICD10 0FB40ZZ, ICD10 OFT40ZZ) and operative urgency (emergent/urgent vs elective) will be based on the admission source for the associated operative encounter. We hypothesize that Black patients are less likely to undergo cholecystectomy in the elective setting than White patients (H1.1), that time to

consultation will modify the effect of race on elective cholecystectomy (H1.2), and that underinsurance (e.g., Medicaid) will exacerbate the effect of race on outcomes.

Financial Outcomes: We will assign costs using data from HPM for billable encounters in the emergency department, inpatient setting and ambulatory procedure units with a primary diagnosis related to symptomatic cholelithiasis and biliary colic within 90-days of diagnosis. Permutations of cost will be assessed with nonparametric tests and regression. We hypothesize that costs will be higher for Black patients and impacted by other SV factors (H1:4). Stratified analysis will be performed by treatment group and point of access.

Analytic Strategy In order to adjust for potential confounders, multivariable regression (logistic and robust) will be used to explain the relationship between race and outcomes. Interaction terms will be used to examine effect modification of social vulnerability factors on the relationship between race and outcomes. The marginal effects of social vulnerability factors will be calculated. All analysis will be performed using STATA Version 17 (Stata Corporation, College Station, TX).

PRELIMINARY STUDY RESULTS and POWER CALCULATIONS

Our preliminary data from Penn Chart demonstrate racial disparities in access to care with a greater proportion of Black PCSL patients undergoing emergent cholecystectomy than White patients (see Equity section). We will be powered at 80% with an alpha of 0.05 to detect differences between Black and White patient outcomes as small as 5%. Note that preliminary data shows a difference of 24% in emergent chole.

[figure not shown]
Telemedicine Consultation as a Mechanism to Improve Surgical Health Equity in Benign Disease (AIM 2)

Design Pragmatic pilot trial.

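### Aim 1 costs stop at 90 days from diagnosis while operations are counted without that limit, so the cost comparison by race can be attenuated, or possibly reversed, if Black patients are operated on later

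*Combined protocol and SAP*

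**What the plan says.** Financial Outcomes (Aim 1) takes costs from the hospital financial dataset for emergency department, inpatient and ambulatory procedure encounters whose primary diagnosis is "related to symptomatic cholelithiasis and biliary colic within 90-days of diagnosis". Hypothesis H1:4, in the same paragraph, is that costs are higher for Black patients. The analysis is by nonparametric tests and regression, stratified by treatment group and point of access.

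Clinical Outcomes (Aim 1) identifies cholecystectomy by procedure code and urgency by admission source. It sets no time limit on either.

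Three other places bear on the window:

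- Aims and Significance gives, as its example of harm from delay, that "patients waiting 20 weeks or more for elective cholecystectomy were more likely to undergo admission for emergency cholecystectomy than those waiting shorter times".
- The Impact paragraph lists "assessing the clinical and financial costs of delays" first among the study's contributions.
- Study Subjects and Eligibility Criteria (Aim 1) admits diagnoses from 1 January 2020 to 30 September 2022 and says that "data will be obtained for January 1 2020 to Dec. 31, 2022".

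The plan gives no reason for the 90 days, names no longer window or sensitivity analysis for cost, and does not mention the cut under Limitations.

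**The concern.** When the question is what delay costs, a fixed window that starts at diagnosis is used up by the delay itself. The longer a patient waits, the more likely it is that the operation falls outside the window. Ninety days is 12.9 weeks; the plan's own example of a harmful wait is 20 weeks, or 140 days, which is 50 days longer.

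The two parts of Aim 1 also stop describing the same events. An emergency operation on day 120 enters the urgency outcome as emergent but adds nothing to cost. If Black patients wait longer, as the study suspects, more of their operative cost is dropped, and the comparison under H1:4 is pulled towards or past zero. A null or reversed cost result could then be read as showing that delay carries no financial penalty.

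**Working it through.** **1. The plan's own figure.** Preliminary data (Equity Plan and Impact): "Black: 65% (76/117); White: 41% (125/303); p<0.001".

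- 76/117 = 64.96% and 125/303 = 41.25%; the difference is 23.7 points, which the plan rounds to 24.
- The chi-square p-value is 1.3 × 10⁻⁵ without continuity correction and 2.1 × 10⁻⁵ with it. The stated figures reproduce.
- The plan gives no effect size or power for cost itself.

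**2. Inputs for the cost illustration.**

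- From the documents: emergent shares p_B = 0.6496 and p_W = 0.4125; D = $6,000, from the cited "mean charge difference over \$6,000".
- Assumed, because the documents give neither: C, the elective cost, and f, the share of a group's operations that fall within 90 days.

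**3. All operations costed.** Mean operative cost per operated patient is C + p × D. The difference is (p_B − p_W) × D = 0.2370 × 6,000 = +$1,422, whatever C is.

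**4. With the 90-day cut.** The counted mean is f × (C + p × D). At C = $10,000 the full means are $13,897 (Black) and $12,475 (White).

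| f Black | f White | Counted difference |
|---|---|---|
| 0.80 | 0.80 | 11,118 − 9,980 = +$1,138 |
| 0.75 | 0.80 | 10,423 − 9,980 = +$443 |
| 0.70 | 0.80 | 9,728 − 9,980 = −$252 |
| 0.80 | 0.75 | 11,118 − 9,356 = +$1,762 |

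The last row shows the opposite case: if White patients' operations are the later ones, the window overstates the difference.

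**5. Where the sign turns.** Reversal needs f_B/f_W < (C + p_W × D)/(C + p_B × D).

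| C | Threshold for f_B/f_W | Relative shortfall in Black patients |
|---|---|---|
| $3,000 | 0.794 | 21% |
| $6,000 | 0.856 | 14% |
| $10,000 | 0.898 | 10% |
| $20,000 | 0.940 | 6% |

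The same can happen through urgency. If emergent operations are captured less often than elective ones at rates common to both groups, the sign turns when f_emergent/f_elective < C/(C + D). That is 0.33, 0.50, 0.63 and 0.77 for the same four values of C.

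**6. Follow-up available.**

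- Entry runs for 366 + 365 + 273 = 1,004 days.
- The last entrant, on 30 September 2022, has 92 days to 31 December 2022.
- A full 180 days is available for diagnoses through 4 July 2022: 366 + 365 + 185 = 916 days, and 916/1,004 = 91.2%.
- Reading that as a share of patients assumes uniform accrual.

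**The case against.** The 90-day window has a visible logic. With at least 92 days of data for everyone, it gives complete and equal follow-up with no censoring method, and it matches the three-month chart review used for Aim 1 covariates. Cost is one of several secondary outcomes, and late emergency operations are still captured clinically. This stands, and it is a reason to keep the 90-day analysis. It is not a reason to have no other, because the constraint binds only the last months of entry.

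A reader might infer more: that late emergency patients count as costing nothing, or that the window will make Black patients look cheaper. The documents support neither.

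- Earlier emergency department and inpatient costs stay in the window; only the late encounter is lost. Late elective operations are lost too.
- The 20 weeks is a wait for elective surgery, not time from diagnosis, and the plan does not say that emergencies cluster after it. Emergencies before day 90 are costed.
- The share of operations after day 90 is given neither by race nor by urgency, so the size and direction of any bias are unknown.
- The $6,000 is a charge difference from cited literature, not a cost from the study's dataset.
- The illustration is per operated patient. The plan does not restrict costs to these, and its Scalability section reports over 9,400 untreated against fewer than 1,000 treated. In the whole cohort, whether patients are operated on at all may matter more than timing.

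The planned stratification by treatment group does not repair the mismatch, since a stratum of emergent operations would mix costed with uncosted ones.

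**Conclusion.** The concern holds as a mismatch between the cost window and the question about delay. Operations after day 90 count clinically and not financially, and nothing else in the plan makes up for it. The consequence is conditional. Equal capture in both groups shrinks the difference without changing its sign. Reversal needs 90-day capture about 6% to 21% lower (relative) in Black than in White patients, for assumed elective costs of $20,000 down to $3,000. Those shortfalls are modest enough to warrant a check, but no figure in the documents shows that they occur. The 90-day result is valid as a 90-day cost; it should not by itself be read as the cost of delay. This is an inexpensive improvement to a secondary outcome.

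**What to change.** Before analysis:

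1. Keep the 90-day cost analysis for the full cohort and label it as cost to 90 days.
2. Pre-specify a 180-day cost analysis for patients diagnosed by 4 July 2022. Alternatively, use all patients with costs to 180 days weighted for administrative censoring at 31 December 2022.
3. Report the share of operations after day 90 by race and urgency, so that the reader can judge how far the two windows should differ.
4. State that the 90-day result alone is not interpreted as the cost of delay, and list the cut under Limitations.

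The cost is a little more analysis. The 180-day complete-follow-up cohort loses 88 of 1,004 accrual days, about 9%; the weighted version loses none but needs a censoring model. No longer extraction period is needed, provided the financial data are drawn for the same dates as the clinical data.

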Scalability Preliminary data from Penn Chart shows that more than 9,400 PCSL patients seen within the last 6 months have a diagnosis of untreated symptomatic gallbladder disease, and less than 1000 have undergone appropriate treatment (see Figure). This proposal will use a robust approach to explain why patients in our community with symptomatic GB disease do not receive timely treatment (Aim1). Then, we will test the ability of telemedicine to improve timely access to surgical care (Aim2). Currently, PCSL and Emergency Medicine providers refer patients to in-person clinic visits with surgeons. These visits typically require at least a half day off from work, if not more. Since the onset of the pandemic, Penn Medicine surgical clinics have integrated telemedicine into routine practice. Telemedicine decreases time off from work and eliminates the need for transportation (two established barriers to surgical care) while promoting surgical health education, the establishment of trust, and ease of communication with the clinic. Patients will be randomized to a telemedicine preoperative surgical consultation or a traditional in-person surgical consultation. The Penn Medicine system has capacity for this volume of surgical referrals across the three downtown hospitals. Patients will be referred to the location that is most convenient for them. This proposal will pilot the use of telemedicine for patients with symptomatic gallbladder disease treated within the community practices of PennMedicine. We propose that, at scale, this initiative will encourage the **development of a Penn Pathway** for symptomatic cholelithiasis and biliary colic to improve patient and provider satisfaction and will show evidence of PennMedicine’s ability to eliminate unnecessary waste in the pathway to surgical health when negotiating **value-based purchasing agreements** with payers.

Equity Plan and Impact

GB disease, associated with obesity, is very common, especially among patients with social vulnerabilities [26, 27]. Guidelines recommend laparoscopic cholecystectomy, a safe and effective same day surgery, for patients with symptomatic cholelithiasis and biliary colic (SGBD). From the literature, we know that delays in care often result in emergent presentation which is significantly associated with increased rates of complications, prolonged hospitalization, and death.[8-10]

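### The Aim 1 regressions make no allowance for practice; if racial mix and outcome rates both vary by practice, the standard error of the race effect will be too small for whole-cohort outcomes

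*Combined protocol and SAP*

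**What the plan says.** The Aim 1 paragraph headed Analytic Strategy states that "multivariable regression (logistic and robust) will be used to explain the relationship between race and outcomes". It adds interaction terms and marginal effects, all in Stata 17. It mentions no random or fixed practice effect, no GEE and no clustered variance.

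The cohort has many sites. Under Study Subjects and Eligibility Criteria, the Primary Care Service Line (PCSL) covers "12 contiguous urban, suburban, and rural counties in the tri-state area of PA, NJ, and DE", and patients discharged from three EDs are also eligible. The Scalability section speaks of "symptomatic gallbladder disease treated within the community practices of PennMedicine". The covariate list has one site-type variable, access point (PCSL or ED), and no practice identifier.

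The power paragraph for Aim 1 says "We will be powered at 80% with an alpha of 0.05 to detect differences between Black and White patient outcomes" down to 5%. It gives no sample size, base rate or design effect.

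**The concern.** A patient-level model treats every patient as an independent observation. Patients of one practice share referring providers and a location, so their outcomes may be correlated. Race is a patient-level variable, and correlated outcomes alone do not distort its standard error. The distortion arises when race is also unevenly spread over practices, because part of the Black-White contrast is then a contrast between practices. A model that ignores practice counts that part as if it rested on thousands of independent patients.

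The word *robust* does not settle the matter. Beside *logistic* it reads as a type of regression. If it means heteroskedasticity-robust standard errors, those do not account for correlation within practices either. If cluster-robust errors are meant, the cluster is not named and no field is listed that would identify it.

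At stake are the false-positive rate of the main race comparison and the width of its confidence interval for whole-cohort outcomes.

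**Working it through.** **The plan's own figure.** The 80% power for 5 points cannot be reproduced exactly, because neither N nor a base rate is given. Inputs available:

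- Equity Plan and Impact: 1,978 Black patients, 21% of those with symptomatic disease. The White count is not given, so 9,400 − 1,978 = 7,422 is used as an upper bound.
- Scalability: "more than 9,400 PCSL patients seen within the last 6 months have a diagnosis of untreated symptomatic gallbladder disease".
- Base rate 41%, borrowed from the preliminary emergent rates "Black: 65% (76/117); White: 41% (125/303); p<0.001".

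With the two-sided pooled formula for two proportions, 41% vs 46% needs [1.96·√(2×0.435×0.565) + 0.842·√(0.41×0.59 + 0.46×0.54)]² / 0.05² ≈ 1,543 per group at 1:1. With 1,978 vs 7,422 the power is 98% and the minimum detectable difference is 3.5 points. Under independence the 5-point claim is therefore attainable for whole-cohort outcomes.

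**Design effect.** For a patient-level covariate and practices of equal size m,

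DEFF = 1 + (m − 1) × ICC(outcome) × ICC(race).

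The naive standard error is too small by a factor √DEFF. The true error of a nominal 5% test is 2·[1 − Φ(1.96/√DEFF)].

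None of the following is in the documents; all are assumptions: N = 9,400; 50, 100 or 200 practices; outcome ICC 0.01 to 0.05; race ICC 0 to 0.4.

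| Practices | m | ICC outcome | ICC race | DEFF | True error |
|---|---|---|---|---|---|
| any | – | any | 0 | 1.00 | 5.0% |
| 200 | 47 | 0.01 | 0.2 | 1.09 | 6.1% |
| 100 | 94 | 0.01 | 0.2 | 1.19 | 7.2% |
| 100 | 94 | 0.02 | 0.2 | 1.37 | 9.4% |
| 200 | 47 | 0.05 | 0.4 | 1.92 | 15.7% |
| 100 | 94 | 0.05 | 0.4 | 2.86 | 24.6% |
| 50 | 188 | 0.05 | 0.4 | 4.74 | 36.8% |

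Middle row written out: 1 + 93 × 0.02 × 0.2 = 1.372; √1.372 = 1.171; 1.96/1.171 = 1.67; two-sided tail 9.4%.

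**Check by simulation.** With 50 practices, 9,400 patients, 400 replicates and no true race effect, a logistic model without covariates other than race gave:

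- race ICC 0: error 5.0% to 5.2%;
- race ICC 0.10 to 0.30 and outcome ICC 0.02 to 0.05: error 8.3% to 26.3% with model-based errors;
- heteroskedasticity-robust errors: the same error rates as model-based errors;
- cluster-robust errors: 5.2% to 6.2%.

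**Effect on the detectable difference** (50 practices, 41% vs 46%). Outcome ICC 0.02 with race ICC 0.10 gives DEFF 1 + 187 × 0.002 = 1.37, power 93% and a detectable difference of 4.1 points. Outcome ICC 0.05 with race ICC 0.30 gives DEFF 3.80, power 54% and 6.8 points, which is above the 5 points claimed.

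**Urgency among operated patients.** The preliminary subset has 117 + 303 = 420 patients. With 100 practices, m = 4.2.

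- ICCs 0.02 and 0.2: DEFF 1.01, error 5.2%.
- ICCs 0.05 and 0.4: DEFF 1.06, error 5.7%.

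If operations are scaled from 6 to 33 months (420 × 33/6 = 2,310, an assumption), the same two settings give 6.0% and 10.3%.

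**The case against.** The strongest reply is that this is a conditional risk. A reader might infer that the standard error *is* too small. The documents do not support that: they give no number or size of practices and do not say how racial mix or referral varies between them. If race is evenly spread there is no inflation. This stands, and the point is worded accordingly.

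Other parts of the reply also stand:

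- The illustrations use unadjusted models. The planned covariates may absorb some of the correlation. How much is unknown.
- The top of the range is demanding. If 6% of patients are operated (an assumption), an outcome ICC of 0.05 means that practice rates run from about 0.8% to 13% between the 10th and 90th percentiles.
- The 9,400 is a six-month count of untreated disease, whereas Aim 1 takes first instances over 33 months. The true N may be larger or smaller.
- Not every patient belongs to a practice, since ED discharges are eligible. Nor do the documents show that practices decide whether consultation or surgery takes place; they also describe patient- and system-level barriers.

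Three further inferences would go too far. One is that every race-by-vulnerability interaction test is inflated; that depends on how each product term clusters and was not examined. Another is that the preliminary 24-point gap is unsafe. Its z is about 4.5, so it would lose significance only at a DEFF above (4.52/1.96)² ≈ 5.3, far from the 1.01 to 1.06 found for 420 patients. The third is that a pooled race effect is the wrong target. Aim 1 asks about the overall disparity, and the pooled effect answers that.

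What the reply does not remove is that the plan is silent on clustering in a cohort drawn from many practices, and that neither natural reading of *robust* supplies it.

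**Conclusion.** The point holds in conditional form, as an inexpensive improvement. The Aim 1 models contain nothing that handles correlation within practices, and the data elements listed would not allow it to be added later. If race and outcome both cluster by practice, the race test on whole-cohort outcomes rejects too often: about 9% instead of 5% at a middle setting (100 practices, ICCs 0.02 and 0.2), and 25% or more only at the extremes. These figures are illustrations that rest on assumed practice counts and correlations and on equal practice sizes. For urgency among about 420 operated patients the inflation is negligible to small; it would grow if the number of operations per practice were several times larger.

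**What to change.** 1. Add the PCSL practice identifier and the ED site to the Aim 1 data elements. The documents do not say that the registry extract already carries a practice field, so this should be confirmed before extraction.
2. Fit all Aim 1 models with standard errors clustered on site of entry (in Stata, vce(cluster …)), with practice as the cluster for PCSL patients. Enter ED site as a fixed effect, and state in advance which cluster an ED-only patient belongs to; the fixed effects alone do not assign one.
3. Say in Analytic Strategy what *robust* means, and that it does not by itself cover clustering. Report the number of clusters.
4. Optionally, add a secondary model with each practice's proportion of Black patients, to separate within-practice from between-practice differences. The pooled race effect can remain the primary estimand.

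The cost is one more extracted field, a rule for ED-only patients, one model option and somewhat wider confidence intervals. If race turns out to be evenly spread over practices, the results should hardly change.
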